8.4 Stopping Criteria

8.4.1 Individual Stopping Criteria

- Participants who develop a Grade 3 toxicity that is assessed by the investigator to be related to the study drug are to be permanently discontinued from study treatment.
- Participants who develop a Grade 4 toxicity, regardless of relatedness to study drug, are to be permanently discontinued from study treatment.
- Subjects who develop Grade 3 or 4 toxicities are to be followed by re-evaluation every 2 days, as feasible, until the toxicity returns to \leq Grade 2 severity.

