8.4.2 Study-Level Stopping Criteria

Study enrollment is to be paused if any of the below criteria are met:

- If ≥ 3 subjects develop the same related Grade 4 (life-threatening) adverse event or laboratory abnormality;
- If ≥ 5 subjects develop the same related Grade 3 or 4 adverse event or laboratory abnormality;
- If ≥ 10 subjects develop any related Grade 3 or 4 adverse event or laboratory abnormality.

Following assessment by the Data Monitoring Committee (DMC, see [Section 10.9](#)), the DMC will determine whether to stop the study, amend the protocol, or continue the study per protocol.

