11.2 Safety Analyses

Safety and tolerability will be assessed in terms of AEs, SAEs, WHO Assessments, and safety laboratory data.

Adverse event data will be descriptively evaluated. All AEs will be reported in data listings. The incidence of post-first dose (treatment-emergent) adverse events will be tabulated by MedDRA preferred term and system organ class, and by severity and relationship to study treatment. All laboratory results and study assessments will be summarized using appropriate descriptive statistics.

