6.1 Time points and Visit Windows

Day 1 is defined as the day of first dose of study drug. Relative days after Day 1 are calculated as (assessment date – Day 1 date) + 1. Relative days prior to Day 1 are calculated as (assessment date – Day 1 date). The day prior to Day 1 is Day -1.

All data will be analyzed using nominal study visits as defined in the Study Schedule and eCRF. No visit windows will be applied for summary and analysis.

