7.7.3 Laboratory Evaluations

Data for the following hematology and chemistry received from central laboratory will be listed and summarized by treatment group and visit. If data for any additional analytes are also recorded, then these will be listed only.

Statistical Analysis Plan

Sponsor Name: Clear Creek Bio, Inc.
Sponsor Protocol ID: CCB-CRISIS-02

Covance Study ID: 000000207395

Hematology	Chemistry
Hemoglobin	Albumin
Hematocrit	Alkaline Phosphatase
Platelets	Alanine Amino Transferase
Neutrophils Absolute	Aspartate Amino Transferase
Lymphocytes Absolute	Total Bilirubin
Monocytes Absolute	Calcium
Eosinophils Absolute	Chloride
Basophils Absolute	Creatinine
Neutrophils %	Glucose
Lymphocytes %	Potassium
Monocytes %	Sodium
Eosinophils %	Total Protein
Basophils %	Lactate Dehydrogenase
White Blood Cell Count	Blood Urea Nitrogen
Red Blood Cell Count (RBC)	Carbon Dioxide/Bicarbonate
RBC Morphology and Mean Corpuscular Volume	C-Reactive Protein

All laboratory data will be reported in International System of Units (SI) units. Out-of-reference-range values will be flagged as high (H) or low (L) in the listings for all laboratory parameters except C-reactive protein.

For analysis purposes, values preceded by a "<" or a ">" sign (i.e. those below or above the limits of quantification) will be considered equal to the lower or upper limit of quantification, respectively.

Laboratory data will be summarized by visit using standard descriptive statistics for the Safety population. Changes from baseline will also be summarized.

For hematology and chemistry parameters, number and percentage of subjects with abnormal results (not clinically significant, clinically significant) at each visit will be provided for each treatment group.

For each laboratory analyte, the baseline value is defined as last scheduled or unscheduled value collected prior to the first dose of study drug. Assessments carried out on day of first study drug administration are considered to have taken place before the study drug administration, if the corresponding times have not been recorded. For post-baseline, only data from scheduled visits will be included in the summary tables.

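### Laboratory tables use scheduled draws only and show no worst grade, so milder off-schedule falls and numeric nadirs appear in listings alone

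*SAP*

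**What the plan says.** SAP 7.7.3 covers hematology and chemistry from the central laboratory: "Data for the following hematology and chemistry received from central laboratory will be listed and summarized by treatment group and visit". Three summaries are planned.

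- Continuous results: "Laboratory data will be summarized by visit using standard descriptive statistics for the Safety population". Change from baseline is added.
- Categorical results: "number and percentage of subjects with abnormal results (not clinically significant, clinically significant) at each visit will be provided".
- The rule on which values count: "For post-baseline, only data from scheduled visits will be included in the summary tables".

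The section plans no toxicity grade, no per-subject worst value and no baseline-to-worst shift. SAP 6.1 works on nominal visits and adds: "No visit windows will be applied for summary and analysis". An unscheduled draw therefore cannot be assigned to a visit and enter a table that way. The listings do carry all central-laboratory values, with high and low flags for every analyte except C-reactive protein.

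The protocol (v5.0) is broader in its wording. Section 11.2 says: "All laboratory results and study assessments will be summarized using appropriate descriptive statistics". Its schedule of events (Appendix A) has hematology and chemistry at Screening and Days 1, 8 and 15, with follow-up to Day 29. Section 9.5.1 allows unscheduled tests to assess adverse events. Under section 8.4.1, Grade 3 or 4 toxicities "are to be followed by re-evaluation every 2 days, as feasible" until they fall to Grade 2 or below.

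**The concern.** Protocol 3.6 names myelosuppression, thrombocytopenia in particular, among the primary dose-limiting toxicities of brequinar. Section 10.8 calls myelosuppression a known effect of the drug's mechanism. Characterising safety is a secondary objective, and the matching endpoint in protocol 6.2 includes laboratory assessments.

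With two scheduled post-baseline draws, each subject contributes at most two post-baseline values per analyte to the tables. The protocol itself produces further values between and after those draws, and the SAP removes all of them from the tables. A subject's lowest count can be one of the removed values. No grade is tabulated even for scheduled values, because the split between clinically significant and not clinically significant is an investigator judgement rather than a DAIDS grade.

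**Working it through.** The plan gives no figure of its own on this point. The check traces where each kind of laboratory value is shown, then sizes what is left over.

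**Step 1. Values the rule removes.** Scheduled post-baseline draws are on Days 8 and 15. Suppose re-evaluation takes place exactly every 2 days.
- Grade 3-4 found on Day 8: repeats on Days 10, 12 and 14, so 3 values are excluded before the next scheduled draw.
- Grade 3-4 found on Day 15: repeats on Days 17, 19, 21, 23, 25, 27 and 29, so up to 7 values are excluded and no scheduled draw follows.

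Tests done to assess adverse events (protocol 9.5.1) are also excluded, in any number.

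**Step 2. Where each kind of value is reported.** Protocol 10 makes a new laboratory abnormality an adverse event if it is Grade 3-4, clinically significant, symptomatic or treated. SAP 7.7.2 tabulates adverse events by maximum grade within system organ class and preferred term.

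| Result at an unscheduled draw | Listing | Adverse event tables | Laboratory tables |
|---|---|---|---|
| Grade 3-4, the fact and its grade | yes | yes, if recorded as required | no |
| Grade 1-2, clinically significant, symptomatic or treated | yes | yes, if recorded | no |
| Grade 1-2, none of these | yes | no | no |
| The numeric nadir, any grade | yes | no | no |

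The last two rows are the gap.

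Protocol 10 also makes a change in severity of a pre-existing abnormal laboratory finding an adverse event. For platelets this adds little, because exclusion criterion 4 bars entry at or below 150,000 per mm³.

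**Step 3. How common the relevant event may be.** Protocol 3.5.2 reports one mild thrombocytopenia in 39 subjects given 100 mg/day or less for 5 days.
- Rate: 1/39 = 2.6%, exact 95% interval 0.06% to 13.5%.
- Expected among about 50 brequinar subjects: 50 × 1/39 = 1.3. Over the interval: 50 × 0.0006 = 0.03 to 50 × 0.135 = 6.7.
- Chance of at least one: 1 − (38/39)^50 = 73%.

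This assumes that the earlier rate carries over. Protocol 8.2.1 describes 39 subjects at this dose level as coming from intravenous oncology studies. The documents do not say what share of cases would be seen only off schedule, so the number lost could be anywhere from none to all of them.

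**Step 4. Effect of one such case on an arm of 50.**
- Rate: 0/50 = 0% against 1/50 = 2%, a shift of 2 points.
- Exact (Clopper-Pearson) two-sided 95% upper limit for 0/50: 1 − 0.025^(1/50) = 7.1%.
- For 1/50: the 97.5th percentile of Beta(2, 49) = 10.6%.

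SAP 7.7.3 plans no such interval. It is used here only as a yardstick for what one case is worth at this sample size.

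**The case against.** The strongest reply is that the protocol already sends the important cases elsewhere. The 2-day re-evaluation applies to Grade 3-4 toxicities, not to every abnormal result. Those are adverse events by definition and are tabulated by maximum grade. An unscheduled test is normally done because an adverse event is already being assessed. Every value is listed. The remainder is a mild, off-schedule fall that the investigator did not consider important. All of this stands, and it limits the point to the last two rows of the table above.

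Three stronger readings are tempting, and the documents do not support them.

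- A reader might infer that the lowest count will usually fall off schedule. The documents give no nadir timing for this regimen, so it *can* be unscheduled, no more. A nadir with no draw near it stays invisible under any table.
- A reader might infer that the pause rule cannot be applied because laboratory grades are not tabulated. That rule, under which enrollment pauses if 10 or more subjects "develop any related Grade 3 or 4 adverse event or laboratory abnormality" (with lower counts for the same event), governs conduct and depends on relatedness. A shift table carries no relatedness. The planned table of drug-related events of Grade 3 or higher does.
- A reader might infer that the SAP contradicts protocol 11.2. That section asks for appropriate descriptive statistics, and by-visit summaries of scheduled values can be read as meeting it. The SAP is narrower, not clearly in conflict.

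The reply does not close the gap. The one prior case at this dose level was mild, the severity for which the adverse event route depends on investigator judgement, symptoms or treatment. Adverse event tables never show a count's lowest value. A listing gives no rate by arm.

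**Conclusion.** The point holds as a reporting gap. Under SAP 7.7.3, no by-arm table would show a numeric nadir at an unscheduled draw. Nor would one show a Grade 1-2 fall in platelets or neutrophils seen only at such a draw and not recorded as an adverse event. Each such case is worth 2 points on an arm's laboratory-table rate at 50 per arm. Adverse event rates are unaffected, and the values remain in the listings.

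This rests on three conditions: about 50 subjects per arm, Grade 3-4 and clinically significant values being recorded as adverse events as protocol 10 requires, and at least some unscheduled draws taking place. It does not mean that severe hematologic toxicity would go unreported. It is an inexpensive improvement to the safety tables rather than the correction of an error.

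**What to change.** In SAP 7.7.3, add a shift table by treatment group from baseline grade to worst post-baseline DAIDS v2.1 grade for platelets, neutrophils, hemoglobin, ALT, AST, bilirubin and creatinine. Use all scheduled and unscheduled central-laboratory values in the Safety Analysis Set. DAIDS v2.1 is already the protocol's grading scale. Keep the by-visit statistics and abnormality counts on scheduled visits only, and state in the section that the two displays use different sets of values.

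The cost is one extra table and the programming to grade the seven analytes, with no new visits or samples. There are two limits. Unscheduled sampling is driven by events, so subjects who are unwell contribute more draws; the table should be read beside the scheduled-visit summaries. The documents do not say where unscheduled repeats are assayed, so any done at a local laboratory would fall outside this table. A footnote should say so.

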7.7.4 Vital Signs

The following vital signs will be listed and summarized by treatment group and visit.

- heart rate (bpm);
- respiration rate (breaths/min);
- body temperature (°C);
- oxygen saturation, SpO₂ (%).

Statistical Analysis Plan

Sponsor Name: Clear Creek Bio, Inc.
Sponsor Protocol ID: CCB-CRISIS-02

Covance Study ID: 000000207395

Vital signs data and changes from baseline in vital signs will be summarized by visit using standard descriptive statistics for the Safety population. The baseline value is defined as last scheduled or unscheduled value collected prior to the first dose of study drug. For post-baseline, only data from scheduled visits will be included in the summary table.

7.7.5 Electrocardiograms

Not applicable.

7.7.6 Physical Examination

Abnormalities identified from physical examination are recorded in the eCRF as Medical History as appropriate and will be listed and summarized as such [See Sections 7.4.1 (Medical History)].

7.7.7 Other Safety Variables

Pregnancy test data will be presented in the subject data listing.

7.8 Interim Analysis

A Data Monitoring Committee (DMC) will be established to provide independent oversight to this trial. The primary responsibility of the DMC will be to review the progress and conduct of the trial in order to maintain scientific rigor and to ensure the wellbeing of subjects participating in the trial. The specific responsibilities of the DMC will be detailed in a separate DMC charter. The DMC will perform periodic data review to assess whether there are clinically significant differences between treatment groups that could affect participant safety. The DMC will review AEs and safety laboratory assessments after the first 20 subjects complete the Day 8 visit, and again after the first 40 subjects complete the Day 8 visit. Following such a review, the DMC Chair will advise the Sponsor that the study be stopped, the design changed, or that the study may continue per protocol.

8. Changes in Planned Analysis

This section is not required at this time, but will be populated in a future approved version of this document.

9. Data Issues

This section is not required at this time, but will be populated in a future approved version of this document

10. References

- 1 ICH. *Statistical Principles for Clinical Trials*, Guideline E9, 1998. Available at <http://www.emea.eu.int/pdfs/human/ich/036396en.pdf>

Statistical Analysis Plan

Sponsor Name: Clear Creek Bio, Inc.
Sponsor Protocol ID: CCB-CRISIS-02

Covance Study ID: 000000207395

- 2 Phillips A and Haudiquet V. *ICH E9 guideline "Statistical principles for clinical trials": a case study.* Statistics in Medicine 2003; 22:1-11
- 3 Brown D J. *ICH E9 guideline "Statistical principles for clinical trials": a case study. Response to A. Phillips and V. Haudiquet.* Statistics in Medicine 2003; 22:13-17
- 4 ICH. *ICH E3 Guideline: Structure and Content of Clinical Study Reports Questions & Answers*, 2012. Available at http://www.ich.org/fileadmin/Public_Web_Site/ICH_Products/Guidelines/Efficacy/E3/E3_QAs_R1_Step4.pdf

11. Appendices

Appendix 1: Document History

Document Version, Status, Date	Summary/Reason for Changes
Version 1, Final, 04 November 2020	Not applicable; the first version
